6 TREATMENT PLAN

Subjects will undergo a thorough pre-study evaluation (see below), and then undergo leukapheresis to generate the DC-based vaccine. Each subject will receive 1 dose of *intra*dermal (*i.d.*) α DC1-based vaccine at weeks 1, 5, 9, and 13 for a total of 4 doses.

6.1 Leukapheresis

Leukapheresis is a minimal risk procedure. All selected subjects will undergo a single 90-120 minute-long limited leukapheresis before vaccination. The product is delivered immediately to the University of Pittsburgh Cancer Institute Immunologic Monitoring and Cellular Products Laboratory from the UPCI Outpatient Clinic pheresis area. Leukapheresed product will be immediately processed as described in the laboratory SOP. The product will be cryopreserved as described in the Chemistry, Manufacturing and Control section of the IND application. If cytopenia (WBC $<$ 2000/mm³, or platelets $<$ 40,000/mm³) develops during, or as a result of, leukapheresis, the procedure will be postponed until recovery. Samples from each cell product will be obtained for hemoglobin, hematocrit, total WBC and differential, and platelet count.

6.2 DC Vaccine Administration

Each dose will consist of a single allogeneic tumor cell vaccine administered intradermally using 1-2 1-mL syringe(s) and needle appropriate for intradermal injections and will hold a total of 0.5 mL of the vaccine preparation. The allogeneic tumor dendritic cell vaccine will be injected in the vicinity of the major nodal basins of the thigh or arm. The nodal basin must not have been dissected.

- Week 1: Both thighs - 1.5 to 2.5 x 10⁶* cells on each side (target: 3-5 x 10⁶ cells total)
- Week 5: Both arms - 1.5 to 2.5 x 10⁶* cells on each side (target: 3-5 x 10⁶ cells total)
- Week 9: Both thighs - 1.5 to 2.5 x 10⁶* cells on each side (target: 3-5 x 10⁶ cells total)
- Week 13: Both arms - 1.5 to 2.5 x 10⁶* cells on each side (target: 3-5 x 10⁶ cells total)

* If the cell count is lower, the total number of cells will be divided equally between the 2 sites. However, at the Investigators discretion, the vaccine may have to be repeated if the cell count is less than $<$ 1.5 x 10⁶/per site.

In the event of a prior node dissection, the priming dose will be administered in the arms.

The vaccine will be administered by the Investigator/Sub-investigator or a member of the advanced practice staff.

Subjects may undergo additional vaccinations, every 3 months (\pm 1 month) if they demonstrate lack of disease progression on week 16 (or later) and if they have vaccine remaining.

6.3 Dose Limiting Toxicities

This study will utilize the NCI CTCAE version 4.0 for toxicity and Adverse Event (AE) reporting (<http://ctep.cancer.gov/forms/>).

The following, if they occur and are felt to be attributable to the investigational treatment, are considered to be dose limiting toxicities (DLT). Any subject experiencing one of these will be taken off study and no further injections will be given:

- \geq Grade 2 or greater bronchospasm,
- \geq Grade 2 or greater allergic reaction or generalized urticaria,
- \geq Grade 2 or greater autoimmune disease
- \geq Grade 3 injection site reaction due to vaccine, implanted port, or catheter
- \geq Grade 3 hematologic and non-hematologic toxicities
- Infection, local or systemic

Management associated with the above adverse events is outlined below. Subject accrual will cease if 2 subjects have a DLT related to vaccine administration. The observation period for DLTs will be 1 week.

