1.1 Primary Objectives

- Feasibility objective: the ability to successfully generate and administer the alpha-DC1 vaccine.
- Safety objective: assess the tolerability and toxicity of the alpha-DC1 vaccine.
- Efficacy objective: evaluate the effect of the alpha-DC1 vaccine on time to PSA progression compared to AA alone. PSA progression is defined as a rise in the PSA value to ≥ 1.0 ng/mL.

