6.4 Study Discontinuation Criteria

Subjects MUST be discontinued from study therapy AND withdrawn from the study for the following reasons:

- Withdrawal of informed consent (subject's decision to withdraw for any reason)
- Any clinical adverse event, laboratory abnormality or intercurrent illness which, in the opinion of the Investigator/Sub-Investigator, indicates that treatment with study therapy is not in the best interest of the subject
- Pregnancy: All WOCBP should be instructed to contact the Investigator/Sub-Investigator immediately if they suspect they might be pregnant (e.g., missed or late menstrual period) at any time during study participation.
- Investigator decides to close the clinical trial prematurely.

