7.2 Evaluation during Treatment

During dendritic cell vaccine cycles (weeks 1, 5, 9, and 13) the following will be performed:

- Complete physical examination (with ECOG performance status and weight)
- Laboratory tests including: CBC, differential, platelet, and chemistry profile each visit (see Section 7.1 and Study Calendar).
- Blood for in vitro assays will be obtained within 1 week after each cycle of vaccination.
- PSA at week 13

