7.3 Post-Treatment

- Complete history and physical examination.
- For subjects with suspected disease progression on therapy, radiographic imaging as indicated.
- PSA at week 17, 21, and every 4 weeks thereafter. Confirmatory PSA should be performed 1 month post progression
- Testosterone at week 17, 25, and every 2 months thereafter
- CBC, differential, platelets at week 25 and every 3 months thereafter
- Chemistry profile (see Section 7.1) at week 25 and every 3 months thereafter
- Blood for in vitro assays (immune parameters of CD4+ and CD8+ T cell responses against tumor-associated and tumor-irrelevant control antigens) will be obtained 1 week and 6 weeks after completion of treatment. The assays will involve the evaluation of cytokine production, cytotoxicity, and changes in cell phenotype of T cell subsets.
- Leukapheresis - a second limited leukapheresis will be performed during week 19 to facilitate immune-monitoring.
- DTH testing (post-testing: 2 to 4 weeks after last vaccine, i.e., during week 15 through 17). The subjects will be asked to agree to the biopsies being taken from the sites of the DTH tests, following their readout.
- EPIMAX analysis may be used to define the magnitude and cytokine production profiles of CD4+ and CD8+ T cell responses to the overlapping peptide libraries and individual peptides covering the entire span of PAP and PSMA molecules
- Subjects with lack of disease progression at 12 months after the last treatment may be monitored for disease free survival, as well as for overall survival.

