7.4 Long Term Follow-up

Patients will continue to be followed after the last vaccine injection and/or progression based upon the timing of their standard of care for their disease.

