7.5 Study Calendar

Screening evaluations are to be conducted within 14 days prior to leukapheresis. Scans and x-rays must be done within 6 weeks prior to the start of therapy.

There is a window of ± 1 week available for scheduling treatment and/or procedures at the discretion of the Investigator/Sub-investigator. This applies also if a course is missed or a subject's treatment and/or testing day(s) need to be rescheduled due to the subject's inability to comply with the study calendar (i.e., hospitalizations, business, vacation plans, travel from long distances for study treatment, in advance of the scheduled date to allow ready access to the result(s), reduce financial burden on the subject [i.e. non-UPMC insurance coverage] or reduce travel inconvenience, illness, transportation issues, holidays, family emergencies, etc.).

Parameter / Week #	Screening	Baseline	Treatment					Post-treatment						
	-4 to -1		1	3	5	9	13	14	15	16	17	19	21	25
Informed Consent	X													
History, PE, ECOG PS	X		X		X	X	X				X		X	X
Serum PSA ^g - every 4 weeks after 12 weeks of hormones	X						X				X		X	X
Serum Testosterone ^k	X										X			X
ANA testing (if clinically indicated)	X													
HIV/viral hepatitis testing	X ^f													
CT scan and Bone Scan ⁱ	X													
CBC, platelets, differential	X		X		X	X	X							X ^h
Chemistry Profile	X		X		X	X	X							X ^h
Leukapheresis (90-120 mins) ^e		X										X ^d		
Skin test (DTH)		X ^b							X ^c		X ^c			
Vaccination ^a			X		X	X	X					X ^a		
Blood (70 cc) for in vitro assays ^j			X		X	X	X							

	Screening	Baseline	Treatment					Post-treatment						
Parameter / Week #	-4 to -1		1	3	5	9	13	14	15	16	17	19	21	25
LHRH Analogue				X										

- a. Subjects may undergo additional vaccinations, every 3 months (± 1 month) if they demonstrate lack of disease progression on week 16 (or later) and if they have vaccine remaining.
- b. DTH placement should be performed within 48-72 hours prior to the day of the first dendritic cell vaccine administration to ensure the test can be read on the day and prior to the first vaccine administration.
- c. DTH testing (post-testing: within 2 – 4 weeks after last vaccine, i.e. week 15 through 17). At the discretion of the investigator/sub-investigator, subjects may be asked to agree to biopsies being taken from the sites of the DTH tests, following their readout.
- d. A second limited leukapheresis will be performed at the end of the study to facilitate immune-monitoring.

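### Sections 6.3 and 6.4 take a man with a DLT or treatment-stopping adverse event off the study, not only off vaccine, and so end his scheduled week 17 to 25 and later safety assessments

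*Combined protocol and SAP*

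**What the plan says.** Section 6.3 lists the DLTs and gives two consequences: "Any subject experiencing one of these will be taken off study and no further injections will be given". It adds: "The observation period for DLTs will be 1 week". Section 6.4 opens: "Subjects MUST be discontinued from study therapy AND withdrawn from the study for the following reasons". Its list puts an adverse event, laboratory abnormality or illness that makes treatment inadvisable in the investigator's opinion alongside withdrawal of consent. Section 6.6 also names unacceptable adverse events as a reason to end treatment, but is silent on whether the man stays on study.

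The post-treatment schedule is in Sections 7.3 and 7.5. Section 7.3 has "CBC, differential, platelets at week 25 and every 3 months thereafter", with the same timing for chemistry. In the Section 7.5 calendar, the row "History, PE, ECOG PS" is marked at weeks 17, 21 and 25 after treatment. Visits during the vaccine course come from Section 7.2, which begins: "During dendritic cell vaccine cycles (weeks 1, 5, 9, and 13) the following will be performed". Section 7.4 says: "Patients will continue to be followed after the last vaccine injection and/or progression based upon the timing of their standard of care".

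Section 1.1 lists among the primary objectives: "Safety objective: assess the tolerability and toxicity of the alpha-DC1 vaccine".

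**The concern.** Stopping a treatment and leaving a study are different acts. A man who has had a DLT should receive no more vaccine, but nothing about the DLT is a reason to stop observing him. Sections 6.3 and 6.4 do both at once.

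At stake is what the trial can report about the course of its most important toxicities: how long they last, whether they resolve, and whether anything follows. The DLT window is one week, so anything later depends on continued observation. Section 3 states that the vaccine aims to induce an autoimmune response against prostate tissue, and Section 6.3 makes autoimmune disease of grade 2 or higher a DLT. Such an event need not run its course within a week.

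**Working it through.** The plan gives no figure on this point. The check sets the rules side by side and counts what the calendar loses.

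**Step 1. Does leaving the study mean more than stopping vaccine?** Section 6.3 names the end of injections as a separate consequence, which would be redundant if leaving the study meant only that. Section 6.4 joins the two with a capitalised AND. Section 6.6 is less explicit but contradicts neither.

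**Step 2. Does another section keep the man on the schedule?**

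| Section | What it provides | Sets safety visits? |
|---|---|---|
| 6.5 | Acute management of fever, pain, hypersensitivity and infection | No |
| 7.4 | Continued follow-up at standard-of-care timing | No |
| 10 | Continuing toxicity review; monthly meetings | No |
| 11.3 | Investigator reports drug-related effects to the sponsor | No |
| 11.4.6 | Sponsor investigates safety information and sends follow-up reports | No |
| 11.5 | Follow-up information goes to the IRB | No |

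These sections cover care, review and reporting. None places a withdrawn man on the 7.3/7.5 assessments.

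**Step 3. What does the calendar lose through week 25?** Safety items in the post-treatment columns of Section 7.5:

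- examinations at weeks 17, 21 and 25: 3
- CBC at week 25: 1
- chemistry at week 25: 1

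After week 25, CBC and chemistry every 3 months are lost as well (7.3; 7.5, footnote h). The skin tests in weeks 15 to 17 and the week 19 leukapheresis serve immune monitoring and are not counted.

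**Step 4. How much of the gap is due to the withdrawal rule?** Let d be the week of the dose that led to the DLT. The DLT window closes at week d + 1.

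- Weeks from window close to week 25: 25 − (d + 1)
- Weeks from window close to the first post-treatment visit, week 17: 17 − (d + 1)
- Difference: 25 − 17 = 8 weeks, whatever d is

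| Dose week d | To week 25 | To week 17 | Due to the rule |
|---|---|---|---|
| 1 | 23 | 15 | 8 |
| 5 | 19 | 11 | 8 |
| 9 | 15 | 7 | 8 |
| 13 | 11 | 3 | 8 |

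The middle column is unscheduled even for a man who stops vaccine and stays on study, because Section 7.2 ties the earlier visits to vaccination. Through week 25, the rule's own effect is therefore the loss of the week 17 to 25 assessments.

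**Step 5. How many men?** Section 9.2 plans 12 subjects. Section 6.3 stops accrual at two vaccine-related DLTs, and 2/12 = 17%. That rule stops new accrual only: men already enrolled could add further DLTs, and withdrawals under 6.4 come on top. The number is still a handful.

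**The case against.** The strongest reply is that no sentence says observation ends. The term used in 6.3 is undefined, and 7.4 promises continued follow-up after the last injection without exception. A man stopped for a DLT has had his last injection, so he could be said to move to standard-of-care timing. The reporting duties in Section 11 also presuppose that someone is following the event. This stands in part. It rules out a reading that a reader might otherwise take, that these men have no follow-up of any kind. It does not supply a schedule: Section 7.4 follows the timing of care for the cancer and names no toxicity assessment.

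A second reply is that the lost assessments are thin. Even a man without toxicity has no scheduled CBC or chemistry between weeks 13 and 25, and a week 17 examination says little about an acute reaction to the first dose. This stands, and it limits the yield of the fix. The assessments have more value for later or persistent events, such as autoimmune ones.

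A third reply is that the main safety result survives. This also stands: the DLT counts towards the accrual stop, and a treatment-related SAE counts in Table 4.

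**Conclusion.** The concern holds at modest size. Followed as written, Sections 6.3 and 6.4 remove the scheduled post-treatment safety assessments from the men whose course matters most for a primary objective. Through week 25 the loss per man is three examinations, one CBC and one chemistry panel, followed by the three-monthly laboratory tests.

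Three stronger readings are not supported:

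- A reader might charge the rule with the whole gap of 23, 19, 15 or 11 weeks. All but 8 weeks of each gap come from stopping the vaccine.
- A reader might add the PSA and testosterone values to the loss. These track disease and hormone recovery, not vaccine toxicity.
- A reader might infer that DLTs or SAEs go uncounted. Nothing in 6.3 or 9.4 removes an observed event.

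The conclusion rests on two readings: that leaving the study ends its scheduled procedures, which is direct but not spelled out, and that the Section 7.2 visits end with the vaccine. No DLT rate is assumed. The power statement in 9.3 and the stopping table in 9.4 do not bear on this point.

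**What to change.** In Sections 6.3 and 6.4, for DLTs and adverse events, replace study withdrawal with permanent discontinuation of vaccine. Unless the man withdraws consent, keep him on the existing post-treatment examinations and laboratory tests through week 25, and follow the event to resolution. Checks before week 17 and event-specific tests would be done as clinically indicated. Bring 7.4 into line.

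PSA and testosterone may be kept for disease and hormone follow-up if the LHRH analogue was given. The Section 5 rule that replaces men who do not complete both courses can stay, since it serves the paired efficacy comparison.

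The cost is protocol wording, a few visits and tests already in the calendar, and possibly some clinically indicated visits, for a handful of men.

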5 STUDY DESIGN AND METHODS

This is a 2 group crossover trial in which subjects are randomly assigned to one of two treatment arms:

Cohort A: 3 months of androgen ablation (AA) to be followed at PSA progression by 3 months of the combination of AA and alpha-type 1 dendritic cell vaccine (DC1).

Cohort B: 3 months of the combination of AA and alpha-type 1 dendritic cell vaccine followed at PSA progression by 3 months of AA.

In this crossover trial each subject will serve as their own control. Following either therapy the time to PSA progression is defined as the time between treatment and the first instance of PSA increase to 1 ng/mL. The endpoint is the difference between the time to PSA progression for the combination of AA + DC1 compared to AA alone. A **total of 12 evaluable subjects** (6 subjects/arm) will be enrolled on the trial. Subjects who do not complete both courses (AA and AA+DCV) will be replaced. This schema will also help us better estimate the time to PSA recovery following 3 months of limited androgen ablation in our cohort of subjects.

All subjects in Cohort B will commence α DC1-based vaccination 2 weeks prior to treatment with the LHRH analogue. Each subject will receive 1 intradermal (*i.d.*) dose of the vaccine at weeks 1, 5, 9, and 13 for a total of 4 doses. The first dose will be considered the ‘priming’ dose and injections on weeks 5, 9, and 13 are ‘booster’ doses. Depending upon cells/volume the injections may utilize 1-2 syringes being administered on a single day. Additional courses of vaccination, if available after the 4 intended protocol doses, can be administered to any subject without evidence of disease progression, every 3 months (\pm 1 month) for up to 12 months. The schema for the vaccine can be found on page 6.

The LHRH analogue (Lupron 22.5 mg or Zoladex 10.8 mg) will be administered 2 weeks after the 1st dose of the DC vaccine.

We assume that 3 months of AA alone will be followed by PSA progression at a median of 6 months with 90% of PSA recovery times between 5 and 7 months. We suspect that a second course of AA will delay time to testosterone recovery by approximately 10% and that testosterone recovery and PSA failure will likely correlate very closely. Therefore we anticipate that a second course of AA will delay time to PSA relapse by approximately 10%. The purpose of randomizing to one of two treatment sequences is to permit an unbiased estimate of

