6.6 Duration of study therapy

In the absence of treatment delays due to adverse events, treatment will continue for at least 4 doses or until one of the following criteria applies:

- Disease progression,
- Intercurrent illness that prevents further administration of treatment,
- Unacceptable adverse event(s),
- Severe reaction to the DTH testing with the tumor cell lysate prior to vaccination,
- Subject decides to withdraw from the study, or
- General or specific changes in the subject's condition rendering the subject unacceptable for further treatment in the judgment of the investigator/sub-investigator.
- Dosing delays > 4 weeks

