9.4 Safety Evaluation

Serious adverse events are uncommon in cancer vaccine trials. For example, no treatment-related deaths or grade 4 toxicities have occurred among 652 subjects enrolled in Phase I studies by CTEP, NCI's Cancer Therapy Evaluation Program (Horstmann et al., 2005). Rather than a separate phase of the study to characterize vaccine safety, we will use continual Bayesian monitoring of SAEs (Berry, 2006) with a stopping rule that permits the investigator to suspend the trial for review by the Data and Safety and Monitoring Committee (DSMC). We have selected prior probabilities of SAEs to conform to our prior beliefs that the probability of a treatment-related SAE, caused by α DC1 vaccine is as low as 5%. The prior probability distribution was selected to permit at most a 10% chance that this prior probability could be double the expected prior probability. Assuming the prior probability follows a beta distribution, the stopping rule will be based on the updated posterior probability of an SAE, which also has a beta distribution. As each subject is observed for an SAE, the posterior probability of an SAE can be calculated. If at any time during the trial the probability is $\geq .50$ that the treatment-related SAE rate exceeds 5%, the study will be suspended pending review by the DSMC. In order to permit continuous monitoring of serious toxicities, a look-up table has been provided (below). This table is based upon cumulative observed SAEs at any point in the trial and can be used to signal when the therapy should be suspended and the trial results reviewed by the DSMC.

TABLE 4. Number of Observed Treatment-Related SAEs and Associated Posterior Probabilities Needed to Suspend the Study

Subjects	Total Observed SAE's	$\Pr(\pi \geq .05)^*$	$B(\text{SAE})^{**}$
1	1	.690	.05
2	1	.675	.098
3	1	.660	.143
4	1	.645	.186
5	1	.630	.226
6	1	.615	.264
7	1	.601	.302
8	1	.586	.337
9	1	.572	.370
10	1	.558	.401
11	1	.543	.431
12	1	.529	.460

π is the posterior probability of a treatment-related SAE. $\Pr(\pi \geq .05)$ is the chance that the posterior probability of a treatment-related SAE given the observed number of subjects treated and observed SAEs, exceeds .05.

** B is the binomial probability of observing at least the number of SAEs in column 2 if the underlying rate of SAE is 5%.

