This table presents the minimum number of SAEs that dictate suspension of the trial in accordance with the stopping rule. According to this table a single SAE due to the α DC1-based vaccine among any of the 10 subjects will trigger suspension and review by the DSMC.

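### At two vaccine-related DLTs, Section 6.3 stops accrual but does not hold vaccine, so men already enrolled can still start or continue it

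*Combined protocol and SAP*

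**What the plan says.** Section 6.3 (Dose Limiting Toxicities) sets two responses. A man with an attributable DLT comes off study and receives no more injections. For the trial, the response is: "Subject accrual will cease if 2 subjects have a DLT related to vaccine administration". The section does not mention vaccine for the other enrolled men and does not ask for committee review. It points to management outlined below, but Sections 6.4 to 6.6 contain only individual discontinuation criteria, supportive care and individual duration rules.

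Section 9.4 (Safety Evaluation) governs treatment-related SAEs. If the posterior criterion is met, "the study will be suspended pending review by the DSMC", and Table 4 "can be used to signal when the therapy should be suspended and the trial results reviewed by the DSMC". A single SAE due to the vaccine "will trigger suspension and review by the DSMC". Earlier in the same section the rule is described as one that permits suspension, so its wording is mixed, but the later sentences are mandatory.

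On timing, Section 5 states: "We assume that 3 months of AA alone will be followed by PSA progression at a median of 6 months". Cohort A starts vaccine only at that point. The four intended doses fall at weeks 1, 5, 9 and 13. Under Section 6.2, "Subjects may undergo additional vaccinations, every 3 months" if disease has not progressed and vaccine remains.

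**The concern.** An accrual stop limits exposure when enrolment and first dose come close together. Here they are separated, by design, for half the men. A Cohort A man enrolled just before the second DLT would not have received any vaccine by then, and nothing in Section 6.3 stops him from starting months later. Once the last man is enrolled, the accrual stop affects only replacements, while Cohort A men may still be awaiting dose 1.

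Tolerability and toxicity are a primary objective (Section 1.1), and Section 6.3 is the only rule that counts DLTs. At stake is whether the response to reaching that limit is prespecified for men still due vaccine or is left to judgement on the day.

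**Working it through.** **Step 1. Does one SAE really suspend the study?** Section 9.4 gives a prior mean of 0.05 and at most a 10% chance that the rate is double that. Solving for a beta prior with mean 0.05 and Pr(π > 0.10) = 0.10 gives Beta(1.695, 32.20). After 1 SAE in n men the posterior is Beta(2.695, 32.20 + n − 1).

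| n | Pr(π > 0.05), recomputed | Table 4 |
|---|---|---|
| 1 | .690 | .690 |
| 6 | .616 | .615 |
| 12 | .530 | .529 |

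All twelve rows agree within .001 and all exceed .50, so one SAE is enough at every tabulated n. Beyond the table it is still enough at 13 (.516) and at 14 (about .50), but not at 15 (about .489).

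**Step 2. Which DLTs does Section 9.4 miss?** Those that are not serious under Section 11.1. That definition includes important medical events without hospitalisation, such as bronchospasm needing intensive treatment at home, so the worse DLTs would probably reach Section 9.4 at the first case. Examples that need not be serious are Grade 2 generalised urticaria, a Grade 3 injection-site reaction and a treated local infection.

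**Step 3. How long can exposure continue after accrual stops?** Take a Cohort A man enrolled the day before. His first dose comes at about 6 months (90% range 5 to 7, Section 5). His week-13 dose follows 12 weeks later: 84 days, or about 2.8 months. So 6 + 2.8 = 8.8 months after accrual closed he could still be receiving intended doses, before any optional ones.

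**Step 4. How often might the limit be reached?** The documents give no DLT rate, so p below is an assumed chance per man of a vaccine-related, non-serious DLT. All men are due vaccine in one period or the other.

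P(X ≥ 2) = 1 − (1 − p)^n − n·p·(1 − p)^(n−1)

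- p = 0.05, n = 12: 1 − 0.5404 − 0.3413 = 0.118
- p = 0.02, n = 12: 1 − 0.7847 − 0.1922 = 0.023
- p = 0.01, n = 12: 1 − 0.8864 − 0.1074 = 0.006
- p = 0.05, n = 16 (upper end of the entry range in Section 4.4): 1 − 0.4401 − 0.3706 = 0.189

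**Step 5. How often would a man still be awaiting his first dose?** This was simulated with 40,000 runs per setting. Assumptions: 12 men at 6:6; even accrual over 6, 12 or 24 months; Cohort A relapse normal with mean 6 months and 90% within 5 to 7; a DLT equally likely at any of the four doses; no dropout. At p = 0.05, the unconditional chance that a second DLT occurs while at least one enrolled man is unvaccinated is 0.086, 0.091 and 0.081 for the three accrual periods. If men 5 to 12 wait until the first 4 have all started vaccine (one reading of the feasibility step in Section 9.2), it is 0.083, 0.086 and 0.073. Under these assumptions, most trials that reach the limit reach it with someone still to start.

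**The case against.** The strongest reply is that this is a graded response, not a flaw: full suspension for a serious event, and closed enrolment plus individual removal for non-serious ones. That is right as far as consistency goes. A reader might infer that Sections 6.3 and 9.4 contradict each other; they do not, because they are triggered by different events. What remains is that the lever in the lower tier does not fit a design with delayed vaccination.

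A second reply is that oversight would act. Section 6.4 requires therapy to stop for everyone if the "Investigator decides to close the clinical trial prematurely". Section 10 provides monthly review, safety modifications and authority to suspend; its wording on treatment is unclear and may have been meant to cover holding vaccine. Section 14.3 requires men to be told of relevant new information. These safeguards are real, so the documents do not support saying that enrolled men are unprotected. But each depends on discretion and none is tied to the DLT count.

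A third reply is that the event is unlikely, and this largely stands. Section 2.4 reports no side effects in the sister melanoma and colorectal trials, Section 2.9 says DC vaccines have not been linked to limiting toxicities, and Section 6.5 expects minimal toxicity. A 10% DLT rate would give 34% for two or more in 12, but no document supports that rate. The 5% in Section 9.4 is a prior for SAEs, so even using 5% for non-serious DLTs is only an illustration.

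A reader might also infer that a hold until the next monthly DSMC meeting would end courses under the Section 6.6 criterion "Dosing delays > 4 weeks". That is weak. Delay runs from the next due dose. With a wait uniform on 0 to 30 days and time to the next dose uniform on 0 to 28 days, the delay exceeds 28 days with probability (½ × 2 × 2) / (30 × 28) = 2/840, or 0.24% per mid-course man. Section 6.6 also opens by setting aside delays due to adverse events.

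Finally, a hold would interrupt men who tolerate the vaccine, with boosters timed around an LHRH depot already given. KLH is only in the first dose, so reactions to priming need not predict booster risk. This is a good reason to let the DSMC decide on mid-course men; it does not justify letting new Cohort A men start before any review.

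**Conclusion.** The point holds as a small, inexpensive improvement to safety. Followed to the letter, Section 6.3 closes enrolment at two vaccine-related DLTs and still lets enrolled Cohort A men start vaccine, and others continue, unless someone intervenes. This conclusion comes from the wording and the crossover timing and does not depend on any assumed rate.

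The scope is narrow: two vaccine-related DLTs, both judged non-serious. The size is illustrative only: about 12% for reaching the limit in 12 men, and 7% to 9% for reaching it with a man still unvaccinated, if the rate were 5%. At 1% to 2% the first figure falls to between 0.6% and 2.3%. These figures show how often the clause could matter. They do not measure harm, or the chance that oversight would fail to act. The test and its error rates are not affected.

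**What to change.** Amend Section 6.3 so that two subjects with a vaccine-related DLT suspend accrual and also hold vaccine administration pending expedited DSMC review. The hold should name new Cohort A vaccine starts first, then remaining scheduled doses and optional 3-monthly doses. State that the DSMC decides whether accrual reopens, whether new starts may proceed and whether mid-course men resume.

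As an optional clarification, note that this hold is not a dosing delay for the purposes of Section 6.6. It removes doubt but is not a main reason for the change.

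The cost is about two sentences of protocol amendment and, if the rule is ever triggered, a short delay to some vaccine starts or doses while the committee meets. Difficulty in replacing men who do not complete both courses (Section 5) already follows from the existing accrual stop and is not a new cost. Sample size and the planned analysis stay as they are.
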